# 8. Study Methods

Study procedures are standardized to the extent possible and all study-related data will be captured on a standardized Case Report Form and entered by sponsor personnel into Clindex, Version 3.11.0.1027R, an electronic data capture software. A copy of the Case Report Form is provided in Appendix B.

### 9. Study Procedures

Patients return for an in-office wound check, a 4-6 week, 3 month and any visit following the 3 month visit depending on the investigator's standard of care for follow up. If the subject is unable to return to the clinical site for all visits, the site may contact the subject or the referring physician to provide follow-up data to study site by telephone.

The following information collected and documented:

- Informed Consent
- Demographic information
- Risk factors for infection
- Implant procedure
- Type of device implanted
- Information on CanGaroo ECM
- CanGaroo ECM related adverse events
- Information on infections

All study-related data will be captured on a standardized Case Report Form. A copy of the Case Report Forms is provided in Appendix B. Case report forms will be sent to Aziyo via email or fax.

[name] Aziyo Biologics, Inc. [name] [contact] Direct Office [contact] Fax [contact]

### **10.** Adverse Event Reporting

#### 10.1 Definitions

#### **Adverse Event (AE)**

Adverse event (AE) will be defined as any untoward medical occurrence, unintended disease or injury or any untoward clinical signs in subjects whether or not related to the device. This includes events related to the device and to the procedure involved. For this post market clinical study only events that relate to the use of the CanGaroo ECM will be collected and is defined below in Adverse Device Effect.

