### Endpoints

The endpoints will be defined as:

- 1. The proportion of subjects with CanGaroo ECM related adverse events.
- 2. The incidence of major pocket infection.

Major infection will be defined as 1) superficial cellulitis in the region of the CIED pocket with wound dehiscence, erosion or purulent drainage, 2) deep incisional or organ/space (pocket) surgical site infection, 3) persistent bacteremia or 4) endocarditis. Minor CIED infections include any that do not meet the definition of a major CIED infection. Documentation will also be provided in the medical records.

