#### Adverse Device Effect (ADE)

An Adverse Device Effect is defined as a clinical sign, symptom, or condition that is causally related to the device procedure, the presence of the device, or the performance of the device. Due to the temporal proximity of the AE to product administration, there is a reasonable possibility that the product may have caused the AE or may have contributed to the severity or duration of an event caused by other means.

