### 10.2 Assessing and Recording Adverse Events

Each AE recorded must be documented on the Case Report Form. All serious and device related events must be reported immediately to Aziyo via telephone or email within 24 hours of the Investigator becoming aware of the event. The case report form will be submitted to Aziyo. The site will be contacted by Aziyo for additional information including, but not limited to:

- Description of the event and underlying cause (diagnosis), coexisting disease, or other. The AE should be recorded in standard medical terminology rather than the subject's own words when possible.
- Date of onset and date of resolution. If the event is present at the single postoperative visit it will be noted as unresolved.
- Intensity of the event: mild, moderate, or severe.
- Frequency of the event: single episode, intermittent, or continuous.
- Action taken: none, medication, procedure, medication and procedure, or other.
- Relationship to the device/procedure/surgery: not-related, possibly-related, or probably-related.

The Investigator must ensure that the details of the event are documented in the medical notes including full details of the outcome, in addition to recording the event on the case report form.

All procedure and device related serious adverse events that are associated with the use of the device will be evaluated in accordance with the protocol and the Sponsor's Incident/Event Reporting SOP. Any serious adverse event that requires a Medical

Device Report will be reported by the Sponsor to the FDA in accordance with Sponsor's Medical Device Reporting SOP. The site should contact:

[name] Aziyo Biologics, Inc. [name] [contact] Direct Office [contact] Fax [contact]

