### 11. Data Analysis

The primary endpoints are as follows:

- 1. The proportion of subjects with CanGaroo ECM related adverse events.
- 2. The incidence of major pocket infection.

Point estimates and exact 95% binomial confidence intervals will be provided for the true (population) values of these two endpoints.

The number and percentage of subjects with AEs and with device-related AEs will be presented by type of AE.

If possible, the rate of major pocket infection will be compared to the rate without use of the CanGaroo ECM device based on data from the U.S. Healthcare Cost and Utilization Project family of databases and/or contemporary literature.

Similarly, if possible, the rate of other AEs will be compared by type to the rate without use of the CanGaroo ECM device based on data from the U.S. Healthcare Cost and Utilization Project family of databases and/or contemporary literature.

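### Section 10.1 limits collection to CanGaroo-related events without exempting infections, while primary Endpoint 2 counts major infection whatever its cause; the protocol should say which rule governs.

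*Combined protocol and SAP*

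**What the plan says.** Section 10.1 (Adverse Event) first defines an adverse event broadly, whether or not it is related to the device. It then narrows what the study gathers: "For this post market clinical study only events that relate to the use of the CanGaroo ECM will be collected". It points to the Adverse Device Effect definition for the meaning of related, which covers a condition "causally related to the device procedure, the presence of the device, or the performance of the device". That definition also reaches events from other causes if the product may reasonably have added to their severity or duration. Section 10.3 includes infection in its list of possible device-related events.

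Section 5 (Endpoints) gives Endpoint 2 as "The incidence of major pocket infection". Major infection is defined by four clinical criteria: superficial cellulitis at the pocket with dehiscence, erosion or purulent drainage, and then "deep incisional or organ/space (pocket) surgical site infection, 3) persistent bacteremia or 4) endocarditis". None mentions relatedness. Section 11 makes this one of the two primary endpoints.

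Section 9 and the synopsis list "CanGaroo ECM related adverse events" and, as a separate item, "Information on infections". Section 12.1 names infection alongside adverse events, as a distinct critical data point to be reviewed with the site. The Case Report Form in Appendix B is a separate document.

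**The concern.** An infection is an untoward medical occurrence, so it meets the 10.1 definition of an adverse event and comes under the collection limit that follows. A site that applies the limit literally has no duty to record a major infection it considers unrelated to the envelope and to the procedure. Endpoint 2 would still count that infection. The protocol therefore states a collection rule that is narrower than the endpoint it must supply, and never reconciles the two.

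What is at stake is the meaning of a primary endpoint. It could be all major infection, or major infection that the investigator judges related. The second is a subset of the first, so any error runs downward. Major infections are likely to be few, so a handful of unrecorded cases would be visible in the estimate.

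**Working it through.** **1. Which text governs infections?** The points on each side are these.

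| Text | Bearing on infections |
|---|---|
| 10.1, Adverse Event | Related events only; no infection exemption |
| 5 and 11, Endpoint 2 and definition | No relatedness condition |
| 9 and synopsis, data items | Related adverse events and infections listed separately; only the first is qualified by relatedness |
| 12.1, data quality | Infection named apart from adverse events |
| 10.2, relationship categories | Include a not-related option, which does not fit a related-only rule |
| 11, tabulations | Adverse events and device-related adverse events both tabulated, which also does not fit |

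Rows 2 to 4 point to all infections being wanted. Row 1 is the only explicit rule on what is collected. Rows 5 and 6 show that the related-only rule is not carried through consistently elsewhere. No sentence states that infections fall outside 10.1.

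**2. Which infections could be left out?** Take the four criteria against the Adverse Device Effect definition.

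- Criterion 1 (pocket cellulitis with dehiscence, erosion or purulent drainage) and criterion 2 (deep incisional or pocket surgical site infection) concern the pocket or the surgical site. A link to the procedure is enough to make them related, so they would rarely be excluded.
- Criteria 3 and 4 (persistent bacteremia, endocarditis) carry no condition on source. A site could attribute either to a remote source and judge it related to neither the device nor the procedure. The exposure lies mainly here.

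**3. How sensitive is the estimate?** The documents give no expected infection rate and no basis for an omission fraction, so there is no plan figure to reproduce. The following is an illustration under assumed counts.

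- Inputs: n = 1000 (the maximum enrolment in Section 6); exact binomial 95% intervals (the Section 11 method); assumed true counts of 5, 10 and 20, that is 0.5%, 1% and 2%; two or three infections not recorded.
- Formula for x events: lower limit = Beta quantile at 0.025 with parameters x and n − x + 1; upper limit = Beta quantile at 0.975 with parameters x + 1 and n − x.

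| True count | All recorded | Two omitted | Three omitted |
|---|---|---|---|
| 5 | 0.5% (0.16 to 1.16) | 0.3% (0.06 to 0.87) | 0.2% (0.02 to 0.72) |
| 10 | 1.0% (0.48 to 1.83) | 0.8% (0.35 to 1.57) | 0.7% (0.28 to 1.44) |
| 20 | 2.0% (1.23 to 3.07) | 1.8% (1.07 to 2.83) | 1.7% (0.99 to 2.71) |

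At an assumed 1%, two or three omissions remove 2/10 to 3/10 of the events; at 2%, 2/20 to 3/20. In every row shown the interval still covers the assumed true rate. The shift is always downward, and the confidence interval does not allow for it.

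**The case against.** The strongest reply is that infections already have their own data stream. Section 9 and the synopsis qualify adverse events by relatedness and leave infections unqualified; if infections were subject to the adverse-event filter, the separate item would be largely redundant. Section 12.1 repeats the separation. Section 10.1 sits in the adverse event reporting section and can be read as governing that stream alone. All sites use one standardized Case Report Form, which may well ask for every infection. This stands as the plainer reading of intent, and it is why no loss of events can be claimed. It does not settle the matter. A short item heading does not say which infections are recorded, and the 12.1 review works on submitted data, so it gives no stated way to find an infection that was never submitted.

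A second reply is that the related-event definition is so broad that little would be excluded. That also stands for pocket infections, and it confines the point to infections attributed elsewhere. Whether such infections belong in an endpoint named for the pocket is a fair question. It should be answered in the endpoint definition, not by a collection rule applied before anyone can check.

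Two stronger readings are tempting. A reader might infer that an envelope with no effect would look protective against external data. Section 11 plans that comparison only if possible and gives no case definition for the external rate, so the documents do not support a statement about its result. A reader might also take the 10.2 sentence "All serious and device related events must be reported immediately to Aziyo" as a further filter on Endpoint 2, since it can mean both conditions or either. That sentence governs 24-hour reporting to the sponsor, not which infections are recorded.

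**Conclusion.** The point holds as an unreconciled conflict between a stated collection rule and a primary endpoint. It is not a demonstrated loss of endpoint events. Section 10.1 is explicit and unexempted, Endpoint 2 is unconditional, and the text that implies all infections are wanted stops short of saying so.

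The exposure is mainly persistent bacteremia or endocarditis that a site attributes to another source. Its size cannot be estimated from the documents. Its direction is known: omission can only lower the Endpoint 2 rate. Under the assumed counts above, two or three missed cases lower the estimate by 0.2 or 0.3 percentage points, which is noticeable against a rate of 0.5% to 2%.

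The conclusion rests on two assumptions: that at least some sites would read 10.1 as covering infections, and that the Case Report Form, which is not part of these documents, does not already ask for all infections regardless of relatedness. If the form does ask for them, the remaining defect is one of protocol wording.

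**What to change.** Add to Section 10.1 and to the Case Report Form instructions:

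- Every infection is recorded whatever its judged relatedness, and relatedness is a separate field.
- Endpoint 2 counts all infections that meet the major-infection definition in Section 5.
- Endpoint 1 counts only events judged related to CanGaroo.

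If the sponsor means Endpoint 2 to leave out infections from a remote source, the Section 5 definition should say so, with those infections still recorded so that the exclusion can be checked.

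The cost is a sentence or two and a line on the form. The downside is a few more events to record and possibly a slightly less favorable observed infection rate. Recording deaths and device removals regardless of relatedness, as a check for missed infections, is optional; it would add data collection beyond this cost.

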#### Adverse Device Effect (ADE)

An Adverse Device Effect is defined as a clinical sign, symptom, or condition that is causally related to the device procedure, the presence of the device, or the performance of the device. Due to the temporal proximity of the AE to product administration, there is a reasonable possibility that the product may have caused the AE or may have contributed to the severity or duration of an event caused by other means.

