# 3. Description

The CanGaroo ECM is constructed from a multilaminate sheet (4-ply) of decellularized, noncrosslinked, lyophilized extracellular matrix (ECM) derived from porcine small intestinal submucosa (SIS). SIS is a natural collagen construct derived from a select layer of tissue that is recovered from porcine small intestine. During processing, the inner and outer muscle layers of the intestine are removed, leaving an intact, decellularized, submucosa with a portion of the tunica propria layer attached to the inner surface. The CanGaroo ECM Envelope will be provided sterile and is intended for single use in a single patient only. Over time, the device will be reinforced by cellular infiltration and tissue growth that will integrate the CanGaroo ECM Envelope.

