### 10.3 Possible Adverse Events

This study will capture events reported following the procedure and at follow up visits as reported by the PI and/or subject and from a review of medical records. The following device-related events have been identified as possible risks from the procedure:

- Allergic reaction to ECM
- Bleeding
- Calcification
- Fever
- Fibrosis
- Hematoma
- Infection
- Inflammation
- Seroma
- Undesired remodeling

There are no identified risks involved in participating in this post-market study.

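### The Adverse Device Effect definition gives two different bases for judging late events, so sites may leave some of them out of Endpoint 1

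*Combined protocol and SAP*

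**What the plan says.** Endpoint 1, one of two primary endpoints in section 11, is "The proportion of subjects with CanGaroo ECM related adverse events". The entry for Adverse Event in section 10.1 then limits what reaches the database: "only events that relate to the use of the CanGaroo ECM will be collected and is defined below in Adverse Device Effect". The ADE definition therefore governs collection as well as classification.

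That definition has two sentences:

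- The first covers a sign, symptom or condition "causally related to the device procedure, the presence of the device, or the performance of the device". It sets no time limit.
- The second reads, in its main part, "Due to the temporal proximity of the AE to product administration, there is a reasonable possibility that the product may have caused the AE", and goes on to include contribution to the severity or duration of an event that has another cause. It gives no window and does not say whether it is a condition, a test or an explanation.

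Three other places bear on the point. Section 3 says of the envelope: "Over time, the device will be reinforced by cellular infiltration and tissue growth that will integrate the CanGaroo ECM Envelope". Section 10.3 introduces its ten event types with "The following device-related events have been identified as possible risks from the procedure"; calcification, fibrosis and undesired remodeling are among them. Section 9 plans a wound check, visits at 4-6 weeks and 3 months, and any visit after that under the site's standard of care.

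**The concern.** The second sentence suits a product given at one moment, whose effects are expected soon afterwards. The envelope stays in place and, on the protocol's own account, is integrated gradually. An investigator who finds pocket fibrosis at a visit after 3 months has two instructions. The first sentence says that the presence of the device is enough if it is the cause. The second, the only guidance on when causation is reasonably possible, points to closeness in time, which the investigator can hardly claim.

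In a study that records every adverse event, a doubtful judgement can be revisited. Here an event judged not to be an ADE need not be submitted. Up to 50 centers may resolve the ambiguity differently, so Endpoint 1 could depend partly on how each site reads one sentence. Section 11 also tabulates device-related events by type and, if possible, compares rates by type with external data. Omitted late events would make both look more favourable.

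**Working it through.** **Figures in the plan.** The protocol gives no expected rate, power calculation or margin for Endpoint 1, so there is no planned figure to reproduce. The main check is a reading of the text.

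**Step 1: does the definition exclude late events?** Take a fibrosis found after 3 months and caused by the envelope.

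| Provision | Result for this event |
|---|---|
| ADE, first sentence | Qualifies: related to the presence of the device, no time limit |
| ADE, second sentence, read as explanation | No effect; still qualifies |
| ADE, second sentence, read as the test of causation | Doubtful or fails: no closeness in time, and no window to check against |
| Section 10.2, relatedness scale | No timing criterion, but it grades only events that have been recorded |
| Section 10.3, list of risks | Named as device-related, with no onset time |

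The event is lost only under the third row. The text neither requires that reading nor rules it out.

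**Step 2: direction of any error.** Let *x* be the number of subjects with at least one related event, *m* the number whose only related events are left out as late, and *N* the number of subjects. The reported proportion is (*x* − *m*)/*N*. Since *m* ≥ 0, this omission can only lower it. A subject who also has a recorded early related event stays in the numerator, so *m* counts subjects, not events.

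**Step 3: scale, on assumed counts.** *N* = 1000 is the enrolment ceiling in section 6. The values of *x* and *m*/*x* are assumptions; the documents give neither. Section 11 specifies exact binomial limits. For *k* = *x* − *m*, these are the 2.5% quantile of Beta(*k*, *N* − *k* + 1) and the 97.5% quantile of Beta(*k* + 1, *N* − *k*).

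| Assumed *x* | Nothing lost | 10% lost | 50% lost |
|---|---|---|---|
| 10 | 1.0% (0.48-1.83) | 0.9% (0.41-1.70) | 0.5% (0.16-1.16) |
| 30 | 3.0% (2.03-4.26) | 2.7% (1.79-3.90) | 1.5% (0.84-2.46) |
| 50 | 5.0% (3.73-6.54) | 4.5% (3.30-5.98) | 2.5% (1.62-3.67) |

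For example, with *x* = 30 and half lost, *k* = 30 − 15 = 15 and 15/1000 = 1.5%. At 10% lost, every interval still contains the full-count rate. At 50% lost, the intervals for *x* = 30 and *x* = 50 no longer do. The planned interval reflects sampling error only and would give no sign of the omission.

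**Step 4: a single event type.** If every case of one type were left out, the table by type would show 0/1000. An exact interval on that would be 0 to 0.37%. This is the extreme case, not a forecast.

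**The case against.** A reader might infer that the definition makes causality depend on timing, so that late events fail it. The documents do not support that. The first sentence is the operative definition and has no time limit. The second contains no requirement and no cut-off. Section 10.3 names calcification, fibrosis and undesired remodeling as device-related and says that events at follow-up visits are captured, from the investigator, the subject and the medical records. A site that reads section 10 as a whole has good reason to report them. All of this stands, and it reduces the point to an ambiguity.

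Three further objections also stand in part:

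- **Infection is largely outside the problem.** Information on infections is a separate collected item (section 9), and major pocket infection is Endpoint 2 with its own definition, which includes some cases of erosion. The exposure is mainly to non-infectious events.
- **Late onset is an inference.** Section 10.3 gives no onset times, and section 3 says only that integration takes place over time.
- **Loss is not certain.** Section 10.2 includes a not-related level and prompt reporting of serious and device-related events, section 11 tabulates all adverse events as well as device-related ones, and section 12.1 has adverse events reviewed with sites. These provisions fit poorly with the collection limit in section 10.1. However, the scale applies to recorded events and section 12.1 describes review of submitted data, so neither reliably recovers an event that a site did not send.

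The objection does not explain why the only stated ground for suspecting causation should be timing.

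**Conclusion.** The ADE definition is internally inconsistent for late events, and because it also controls collection, the inconsistency can affect a primary endpoint. The likely victims are late non-infectious tissue events found at the 3-month visit or after. Any resulting bias in Endpoint 1 is downward. Its size cannot be estimated, because the documents give neither the event rate, nor the share of events that occur late, nor how sites will read the second sentence.

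The conclusion rests on two assumptions: that some related events appear late, and that some sites treat the second sentence as the test. Neither is shown by the documents, and both are plausible. It would go too far to say that the plan excludes such events, or that Endpoint 1 is already distorted. The wording should be changed because prevention is nearly free and an unsubmitted event cannot be restored at analysis.

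**What to change.** In section 10.1, keep the first sentence of the ADE definition unchanged and replace the whole of the second with:

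> An event is considered causally related if, at any time after implant, there is a reasonable possibility that the device procedure, or the presence or performance of the CanGaroo ECM, caused the event or contributed to its severity or duration; a long interval since implant is not by itself a reason to judge an event unrelated.

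Replace the full sentence: deleting only its opening clause would leave an unconditional statement that the product may have caused the event. The new text keeps the device procedure, so it agrees with the first sentence.

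Also state that the event types listed in section 10.3 are recorded on the case report form whenever found during follow-up, with relatedness graded on the section 10.2 scale: "Relationship to the device/procedure/surgery: not-related, possibly-related, or probably-related". Two edits follow from this. The collection limit in section 10.1 needs a matching exception. Section 11 should say which levels of the scale count in Endpoint 1, which the plan does not state now.

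The cost is a short protocol change, a site memo and slightly more event recording, with no added visits. The Endpoint 1 rate may become slightly less favourable.
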